8.0 DATA MANAGEMENT AND INTEGRITY

8.1 Data Completion and Record Keeping

Source Documents

Source documents are documents on which information regarding subjects is first recorded, including printed, optical, or electronic documents. Investigator subject files or hospital records generally are the basis of source document information. This includes, but is not limited to, the following: original subject files; hospital/clinic records; original recordings/tracing; digital images from automated instruments (e.g., cameras); radiographs; device accountability records; photographic negatives; and, records kept at the investigation site, at the laboratories, and at other departments involved in the clinical investigation. Assessments made by the central review committee that are directly entered into the CRFs may also be considered as source documents.

Other source data comes from NeuWave Medical's Call Home Database. The NEUWAVE FLEX Ablation System has a functionality that electronically collects procedure data and information during the ablation procedure and is transmitted by the NEUWAVE Ablation System to NeuWave Medical, Inc., after the conclusion of each ablation procedure; this information is collectively called the "Call Home Database." The procedure data include, but are not limited to, the following: date and time of procedure, anatomical location of ablations, number of ablation cycles and power used for each ablation, number of probe placement attempts per ablation, type of probes used, and type of anesthesia. Some of these relevant ablation procedure details will be provided to the site via a report generated from Call Home Database called a Call Home Report. The study site will review the report for accuracy and enter the procedure details into the study's clinical database. Reports generated from the Call Home Database must be retained by the Investigator as part of the subject's permanent medical record. The report should be retained for review and source data verification by the monitor. If a site is unable to receive the report generated from the Call Home Database, the relevant ablation procedure details should be manually recorded in the source documents from what is displayed on the NeuWave System monitor screen.

All applicable scans (i.e., cone beam CT scans (taken during the ablation procedure), all conventional CT scans (taken during the post-ablation follow-up visits), and applicable PET scans should be de-identified and uploaded to the study imaging database in DICOM (digital imaging and communications in medicine) format, if possible. The imaging database will be controlled and maintained by the same vendor that organized and contracted the Central Review Committee, [REDACTED]

[REDACTED] The Sponsor will have "read-only" access to the imaging database during the study. Separate instructions for the site to de-identify and upload all applicable scans will be provided in a separate document.

Also, only for those subjects who specifically consent, some ablation procedures may be filmed for training and educational purposes.

Source documents must be retained by the Investigator as part of the subject's permanent medical record. The information in the source documents is used to complete the eCRFs. All

information captured on the eCRFs should be completely and accurately supported in source documentation. Any additional information relevant to the study should be included in the source documents. Particularly, any deviations from the protocol or procedures should be recorded in the source documents. The Investigator will retain originals of all source documents, subject consent forms, and study data.

Electronic Data Capture

An EDC system will be used by site personnel to transfer data from source records (medical records and/or source document worksheets) onto common eCRFs. This system is a web-based, secure electronic software application [REDACTED] [REDACTED] [REDACTED]

[REDACTED]. This system was designed and is developed and maintained by [REDACTED] in a manner that is compliant with national and international GCP data protection/data privacy and electronic record/electronic signature (e.g., 21 CFR Part 11) regulatory requirements. The EDC system will be used to facilitate the collection of all data at the site. Designated site personnel will be responsible for entering subject data into the EDC system. All external and Sponsor internal users will be trained on the EDC application at a level dependent on their planned function. An EDC digital User Manual will be available under the help menu within the [REDACTED] website to assist in the collection and entry of source data into the electronic casebook.

A 24/7/365 Help Desk Support line [REDACTED]

[REDACTED] staffed by the outsourced vendor will also be available to respond to site and monitor questions.

Data Collection

Each EDC eCRF will be completed by the PI or PI's designee. Every effort should be made to respond to all monitoring and/or data management questions on each eCRF as completion of the data is required by the protocol. A unique ID number will identify each subject. The subject's unique study ID number will be visible on each eCRF. At no time should the subject's name appear on the eCRFs.

All data should be recorded accurately and completely. The Investigator is responsible for reviewing and approving each completed eCRF. The Investigator will document assurance of overall review and approval by electronically signing each subject's electronic casebook.

Data Correction

Required data corrections to eCRFs will be prompted via automated electronic edit checks and/or queries manually created by Sponsor reviewers. The change, the person making the change, and the time the change was made to the eCRFs will be automatically captured in the audit trail [REDACTED].

Data Privacy

The collection, use, and disclosure of all personal data, including subject health and medical information, are to be maintained in compliance with applicable personal data protection and security laws and regulations that govern protected health information and the informed consent given by each subject. When collecting and processing such personal data,

appropriate measures are to be taken to maintain the confidentiality of subject health and medical information and to prevent access by unauthorized persons.

None of the data collected and transmitted by Call Home Database is attributable to an identifiable subject.

Record Retention, Inspection, and Custody

The Investigator must maintain all documentation related to the study until notified by the Sponsor. The Investigator will allow representatives of the Sponsor, the FDA, or other government regulatory agencies to inspect all study records, eCRFs, and corresponding portions of the subject's office and/or hospital medical records at regular intervals during the study. These inspections are to verify adherence to the protocol, integrity of the data being captured on the eCRFs, and compliance with applicable regulations.

Study reports will not identify subjects by name. These reports may be submitted to the FDA and/or regulatory authorities.

If custody of the clinical study records is transferred, notice of such a transfer should be given to the Sponsor no later than 10 working days after the transfer occurs.

8.2 Medical Dictionary Coding

Medical dictionary coding of medical history and verbatim AEs captured on eCRFs will be performed using a coding thesaurus algorithm. The Medical Dictionary for Regulatory Activities (MedDRA) and WHO Drug dictionaries will be used after data entry and query resolution, via auto-encoding and interactive coding processes.

8.3 Data Quality Assurance

Steps to be taken to assure the accuracy and reliability of data include the selection of qualified investigators and appropriate sites, review of protocol procedures with the Investigator and associated personnel prior to the study, and periodic monitoring visits by the Sponsor. The Sponsor will review eCRFs for accuracy and completeness during monitoring visits (onsite or offsite); any discrepancies will be resolved with the Investigator or designees, as appropriate.

8.3.1 Investigator Training

Prior to screening subjects for this study, the PI, sub-Investigators, study coordinators, and other designated staff (as applicable) will be provided information on study execution, data collection, and procedures specific to this clinical protocol. All training, and retraining, if necessary, will be documented accordingly and filed.

8.3.2 Monitoring

This study will be monitored by the Sponsor to ensure the following:

- The rights and well-being of the subjects are protected.
- The reported data is accurate, complete, and verifiable from source documents where utilized.
- The conduct of the study is in compliance with the currently approved protocol/amendment(s), applicable GCPs, and with applicable local/regional regulatory

requirements.

The extent and nature of monitoring will be predetermined and agreed to by the Sponsor and investigators. Monitors will comply with established written standard operating procedures as well as procedures specified by the Sponsor for monitoring this study as characterized in the Monitoring Plan.

9.0 DEVIATIONS FROM THE PROTOCOL

A protocol deviation is any noncompliance with the registry protocol, Good Clinical Practice, or protocol-specific requirements. A deviation (any activity conducted outside the parameters established by the protocol) can be identified from a number of sources. Potential sources include but are not limited to: a member of the Investigator's staff, a Sponsor representative during monitoring visits, or a member of the data management or statistical groups when entering or analyzing data. Regardless of the source, it is crucial to document the deviation in the protocol deviation eCRF. The Investigator will report protocol deviations to the IRB/EC as required by the IRB/EC procedures.

Any deviation from the protocol or procedures should be recorded in the source documents. Assessments or visits that are not completed because they are not SOC at a site should not be considered protocol deviations if the protocol specifies that the assessment or visit is only to be collected if SOC.

Steps to be taken to assure the accuracy and reliability of data include the selection of qualified Investigators and appropriate sites, review of protocol procedures with the Investigator and associated personnel prior to the study, and periodic monitoring visits by the Sponsor. The Sponsor will review eCRFs for accuracy and completeness during monitoring visits; any discrepancies will be resolved with the Investigator or designees, as appropriate. All deviations to the protocol requirements should be documented in the source as well as the protocol deviation eCRF.

10.0 STATISTICAL METHODOLOGY

10.1 Statistical and Analytical Plans

The Sponsor Data Management and Biostatistics groups will be responsible for the analysis of data from this protocol. A comprehensive and detailed Statistical Analysis Plan (SAP) will be finalized prior to database lock to supplement the statistical design and analysis described in this section.

Categorical variables will be summarized descriptively by frequencies and associated percentages. Continuous variables will be summarized descriptively by number of subjects, mean, standard deviation, median, minimum, and maximum.

10.2 Study Design

This is a prospective, multicenter, single-arm study.

10.3 Ablation Assignment

This is a single-arm study where all enrolled subjects will receive the same ablation procedure: transbronchial microwave ablation using the NEUWAVE FLEX MC Microwave Ablation System and Accessories for oligometastatic tumors ($\leq 2\text{cm}$) in the lung. There will be no blinding or randomization.

10.4 Interval Windows

Interval windows are provided in Table 1: Schedule of Assessments. No additional windows are planned for analysis purposes.

10.5 Primary Endpoints and Associated Hypotheses

The following hypotheses will be evaluated in this study:

$$H_0: p \leq 0.80 \text{ vs.}$$

$$H_1: p > 0.80$$

where p represents the true 30-day Technique Efficacy rate of FLEX MC and 0.80 is the performance goal, which was determined through an internal systematic literature review and meta-analysis of microwave and radiofrequency ablation systems used in the treatment of lung tumors.

10.6 Levels of Significance

A one-sided significance level of 0.025 will be used to test the hypotheses above. No other formal hypothesis tests are planned for this study and estimation for all other endpoints will be performed using two-sided 95% confidence intervals.

10.7 Analysis Sets

The primary analysis of safety and effectiveness endpoints will be performed on the Full Analysis Set, defined as all subjects who are enrolled in the study and receive ablation. A Per Protocol analysis set will be defined as all subjects who have undergone the ablation procedure

and have no major protocol deviations. Effectiveness analyses will be repeated for the Per Protocol Set.

10.8 Sample Size Justification

10.9 Analyses to be Conducted

Analyses described below will be performed on all enrolled and ablated subjects.

Disposition of Study Subjects

Subject disposition will be summarized using counts and percentages. The number and percentage of subjects completed and discontinued along with the specific reasons for discontinuation will be tabulated by ablation group and in total.

Demographic and Baseline Characteristics

Summary statistics will be provided for subject demographics and pre-operative ablation characteristics.

Primary and Secondary Endpoint Analyses

The number and percentage of tumors achieving Technique Efficacy will be summarized and a 95% confidence interval will be estimated. Hypothesis testing for the primary endpoint will be performed using the methodology described in the previous section. The number and percentage of tumors achieving Technical Success will also be summarized, and a 95% confidence interval will be estimated. Local Tumor Progression will be summarized in a similar manner. Only target lesions will be included in the primary endpoint analysis for Technique Efficacy and primary summaries of Technical Success and local Tumor Progression. Data collected on non-target tumors for these endpoints will be summarized separately and not included as part of the primary analysis. The analysis of target tumors for these three endpoints will also include a subject level summary that will be secondary or supportive to the tumor level analysis.

Summary statistics will be provided for other secondary endpoints, as appropriate, for continuous or categorical variables. Local Tumor Progression Free Survival, Progression Free Survival, and Overall Survival will be estimated using the Kaplan-Meier method and confidence intervals will be provided.

The number and percentage of subjects experiencing perioperative AEs (time of consent through 30 days of any ablation procedure), device- and procedure-related AEs (30 days post any ablation procedure through the end of the study or early discontinuation) and all SAEs (time of consent through the end of the study or early discontinuation) will be summarized by MedDRA system organ class and preferred term. A similar summary will also be provided for all SAEs from Visit 3 (the first post-ablation visit) through Visit 6 (end of study) as well as for the entirety of the study (Visit 1 – Visit 6). Ninety-five percent confidence intervals may be provided for pre-specified adverse events of interest, which are:

1. Pneumothorax (overall and CTCAE grade ≥ 2)
2. Hemorrhage, bleeding requiring medical intervention (CTCAE grade ≥ 2)
3. Chest wall pain
4. Pleural effusion or empyema (overall and requiring chest tube drainage)
5. Pneumonia
6. Pulmonary abscess
7. Other lower-tract respiratory infection

8. Bronchopleural fistula.

The Numeric Pain Rating Scale scores will be summarized with methodology consistent to the recommendations of the specific survey. Additional endpoints will be summarized with descriptive statistics.

Plans for Interim Analysis

There are no plans for any formal interim analyses with intent to stop the study early or to modify the study design. However, non-formal interim analyses are planned. The first interim analysis will occur after 20 subjects complete Visit 3 (30 days) and will be descriptive in nature only and will not impact the final analysis. The second interim analysis will occur after all subjects complete Visit 3 (30 days) and will include an evaluation of the primary endpoint against the performance goal as well as provide a summary of all baseline and procedural-related data. A complete summary of all safety-related data observed through the duration of follow-up on all subjects will also be provided. The intent of this analysis will be to support regulatory filing activities where appropriate.

An additional interim analysis may be performed after all subjects have completed Visit 5 (6 months). The final analysis will be completed once all subjects have completed Visit 6 (12 months) and will summarize all endpoints collected during the trial.

Complete details for all planned analyses will be included in the study SAP, which will be finalized prior to database lock.

Analysis of Safety

The analysis of safety is summarized above under Primary and Secondary Endpoint Analyses.

Handling of Dropouts or Missing Data

The primary endpoint analysis of Technique Efficacy at Visit 3 (30 days post-ablation) will be performed on observed data only. It is anticipated that dropout before the 30-day visit will be unlikely. However, several sensitivity analyses will be performed for the primary endpoint to assess the robustness of the conclusion based on observed data. This will include a worst-case assumption where all subjects not completing Visit 3 will be assumed to have not achieved Technique Efficacy. A tipping point analysis and multiple imputation will also be considered as alternatives to handling missing data. Time-to-event analyses will use standard censoring assumptions for the handling of subjects who do not complete follow-up visits. Complete details on sensitivity analyses for the primary and secondary endpoints will be provided in the SAP.

Analysis of Subgroups

At a minimum, subgroup analyses are planned to be performed by original histology and tumor size. Additional subgroups may be identified pending the distribution of baseline demographic or clinical characteristics. All subgroup analyses will be descriptive in nature and summary statistics will be provided for procedure-related parameters and time-to-event endpoints and adverse events.

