	
Technical Success, Repeat Ablation Efficacy, and Hospital Readmission Rate will be summarized in a similar manner. Local Tumor Progression, Local Tumor Progression Free Survival, Progression Free Survival, and Overall Survival will be estimated using the Kaplan-Meier method and confidence intervals will be provided.
 
The number and percentage of subjects experiencing device-related AEs will be summarized by the MedDRA system organ class and preferred term. A similar summary will also be provided for procedure-related AEs and all SAEs.
 
Summary statistics will be provided for all other endpoints as defined within the protocol.

Interim Analyses	
The first interim analysis will occur after 20 subjects complete Visit 3 (30 days) and will be descriptive in nature only and will not impact the final analysis.
 
The second interim analysis will occur after all subjects complete Visit 3 (30 days) and will include an evaluation of the primary endpoint against the performance goal as well as provide a summary of all baseline and procedural-related data. A complete summary of all safety-related data observed through the duration of follow-up on all subjects will also be provided. The intent of this analysis will be to support regulatory filing activities where appropriate.
 
An additional interim analysis may be performed after all subjects have completed Visit 5 (6 months).
 
The final analysis will be completed once all subjects have completed Visit 6 (12 months) and will summarize all endpoints collected during the trial.

Time and Events Schedule	See Table 1 on the next page.

Table 1: Schedule of Assessments

Visit No.	Visit 1	Visit 2			Visit 3	Visit 4	Visit 5	Visit 6	Unsched. Visit ²¹
Visit	Screening	Pre-Procedure	Intra-Procedure	Post-Procedure	Follow-up	Follow-up	Follow-up	Follow-up	
Interval Windows	≤ 30 days pre-ablation	Day 0	Day 0	Day 0 - Discharge	30 days (-7 to +14 days)	3 months (±2 weeks)	6 months (±1 month)	12 months (±1 month)	
Standard Study Assessments									
Informed Consent	X								
Inclusion / Exclusion Criteria	X	X							
Demographics	X								
Medical / Surgical History ¹	X								
Concomitant medications ²	X	X		X	X	X	X	X	X
Concomitant procedures	X	X		X	X	X	X	X	X
BMI	X								
Key Vitals ³	X	X		X	X	X	X	X	
ECOG Status	X	X			X	X	X	X	
Pulmonary function tests (PFTs)	X					X	X	X	
Laboratory Assessments									
Pregnancy test ⁴	X	X							
Coagulation tests ⁵	X	X ⁶							
CBC with differential	X								

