4.3 Secondary Endpoints

- Technical Success: All A0 and A1 ablation classification determinations (complete tumor ablation with a surrounding minimal margin) as assessed by cone beam CT imaging, immediately following the ablation procedure.
- Navigational Success: Successful navigation to the targeted peripheral lung tumor(s) as confirmed using cone beam CT (CBCT).
- Local Tumor Progression (LTP): Recurrence of originally ablated target tumor(s) within or abutting the ablation zone using 30-day post-ablation imaging as the baseline. Measuring progression details will be outlined in a separate Imaging Charter.
- Local Tumor Progression Free Survival (LTPFS): Time from the ablation until local tumor(s) progression (LTP) or death, whichever occurs first. Measuring progression details will be outlined in a separate Imaging Charter.

- Progression Free Survival: Time from the original ablation until tumor(s) progression or death, whichever occurs first (includes local, regional, or distant progression). Measuring progression details will be outlined in a separate Imaging Charter.
- Disease (cancer) Specific Survival: Time from the original ablation until death from the treated primary malignancy.
- Overall Survival: Time from the original ablation until subject death (includes death from any cause).
- Repeat Ablation Efficacy Rate: Rate of original tumors that have been re-ablated successfully (i.e., Technical Success of tumors that have been re-ablated/all original tumors that have been re-ablated).
- Change in all available PFTs (pulmonary function tests) from pre-ablation baseline values to values at 3 months, 6 months, and 12 months post-ablation.
- Change in overall health-related quality of life (HRQOL) and sub-scales, including physical functioning and pain domains, per the validated EORTC QLQ-C30 and QLQ-LC13 questionnaires throughout the duration of the study.

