**Time to Event Endpoints:**

Local Tumor Progression Free Survival (LTPFS) is defined as: Time from the ablation until local tumor(s) progression (LTP) or death, whichever occurs first.

Progression Free Survival (PFS) is defined as: Time from the original ablation until tumor(s) progression or death, whichever occurs first (includes local, regional, or distant progression). Specifically: For local tumors, time from the original ablation until tumor(s) progression or death, whichever occurs first. For regional and distant tumors, time from study day 0 or last local therapy (if treated after study initiation) until tumor(s) progression or death, whichever occurs first.

Disease (cancer) Specific Survival (DSS) is defined as: Time from the original ablation until death from the treated primary malignancy.

Overall Survival (OS) is defined as: Time from the original ablation until subject death (includes death from any cause).

Local Tumor Progression Free Survival (LTPFS), Progression Free Survival (PFS), Disease Specific Survival (DSS), and Overall Survival (OS) will be estimated using the Kaplan-Meier method with 95% confidence intervals provided at month 12. The time from the day of the initiation ablation procedure to the specific event will be derived.

Patients who are re-ablated are considered as reaching an event respectively for each of the LTP, LTPFS and PFS event definitions.

Patients without a progression event, as defined above, will be censored by the last contact date (the last date in the study).

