### **8.13 Handling of Missing Data**

No imputation will be used for missing data or early dropouts in all analysis except in the sensitivity analyses for the primary endpoint (see Section 8.8.1). Time-to-event analyses will use standard censoring assumptions for the handling of subjects who do not have event or do not complete follow-up visits (see Section 8.8.2).

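### SAP 8.8.2 estimates Disease Specific Survival by Kaplan-Meier without providing for deaths from other causes, so 1 minus the curve slightly overstates the month-12 probability of cancer death

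*Protocol*

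**What the plan says.** Protocol 4.3 defines DSS as "Time from the original ablation until death from the treated primary malignancy", and SAP 8.8.2 uses the same definition. No other kind of death is an event.

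The Protocol names no estimator for it. Section 10.9 lists three endpoints for Kaplan-Meier: "Local Tumor Progression Free Survival, Progression Free Survival, and Overall Survival will be estimated using the Kaplan-Meier method and confidence intervals will be provided". The Protocol Summary has a slightly longer list, again without DSS: "Local Tumor Progression, Local Tumor Progression Free Survival, Progression Free Survival, and Overall Survival will be estimated using the Kaplan-Meier method". For the remainder, 10.9 says "Summary statistics will be provided for other secondary endpoints, as appropriate, for continuous or categorical variables". Sections 10.1 and 10.9 leave full detail to the SAP.

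SAP 8.8.2 supplies the method: "Disease Specific Survival (DSS), and Overall Survival (OS) will be estimated using the Kaplan-Meier method with 95% confidence intervals provided at month 12". SAP Section 5 also names DSS among the four endpoints given month-12 intervals if the primary endpoint meets its goal. It plans no formal test for DSS.

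On censoring, Protocol 10.9 says "Time-to-event analyses will use standard censoring assumptions for the handling of subjects who do not complete follow-up visits". SAP 8.13 says "Time-to-event analyses will use standard censoring assumptions for the handling of subjects who do not have event or do not complete follow-up visits". The one explicit rule in SAP 8.8.2 sets the censoring date, last contact, for patients who have had no progression event; it is not written for DSS. Neither document mentions competing events or cumulative incidence.

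**The concern.** For overall survival and the two progression-free endpoints, every death is an event, so Kaplan-Meier raises no such question. DSS differs because a death from another cause makes the event impossible. Such a subject does not have the DSS event, so standard censoring would remove the subject at the date of death. Kaplan-Meier then in effect redistributes that subject's future risk among those still alive, as if the subject could yet die of the cancer.

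One minus the resulting curve is not the share of treated subjects who die of their cancer by month 12. It is at least that share, and larger whenever other-cause deaths come before cancer deaths. Nor does it combine with other-cause mortality to give 1 minus overall survival. A reader of the clinical study report would probably take the month-12 figure as the plain probability.

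Other-cause death is a real possibility here. Protocol 3.0 reports that one of the 10 subjects in the sponsor's pilot died periprocedurally, probably from the procedure.

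**Working it through.** The documents give no expected DSS rate and no 12-month death rate, so there is no plan figure to reproduce. The sizes below are illustrations under stated assumptions.

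**Inputs**
- Three-year overall survival of about 45-65% for thermal ablation and SBRT (Protocol 3.0, from a published meta-analysis).
- Constant hazards (assumed).
- Share *f* of deaths not from the cancer: 20% to 50% (assumed).
- 145 ablated subjects (Protocol 5.2).

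**Step 1. Twelve-month mortality.** S(1) = S(3)^(1/3).
- S(3) = 0.65: S(1) = 0.866, mortality 13.4%, total hazard H = −ln(0.65)/3 = 0.144.
- S(3) = 0.45: S(1) = 0.766, mortality 23.4%, H = −ln(0.45)/3 = 0.266.

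**Step 2. The two quantities at month 12.**
- Cumulative incidence of cancer death: CIF = (1 − f)(1 − exp(−H)).
- Kaplan-Meier with other-cause deaths censored: 1 − KM = 1 − exp(−(1 − f)H).

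| S(3) | f | CIF | 1 − KM | Overstatement (points) |
|---|---|---|---|---|
| 0.65 | 0.2 | 10.70% | 10.85% | 0.15 |
| 0.65 | 0.5 | 6.69% | 6.93% | 0.24 |
| 0.45 | 0.2 | 18.70% | 19.18% | 0.48 |
| 0.45 | 0.5 | 11.68% | 12.46% | 0.78 |

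**Step 3. Early other-cause deaths.** Suppose a fraction *e* dies of the procedure at the start and all later deaths are from the cancer, with hazard H. Then 1 − KM = 1 − exp(−H), CIF = (1 − e)(1 − exp(−H)), and the difference is e(1 − exp(−H)).
- e = 3%: 0.03 × 13.4% = 0.40 to 0.03 × 23.4% = 0.70 points.
- e = 10%: 1.3 to 2.3 points.

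**Step 4. The same effect in counts, against precision.** Take 145 subjects, complete 12-month follow-up and 15 cancer deaths (assumed). The cumulative incidence is 15/145 = 10.3%. With *d* other-cause deaths before any cancer death, 1 − KM = 15/(145 − d):
- d = 2: 15/143 = 10.5%
- d = 5: 15/140 = 10.7%
- d = 14: 15/131 = 11.5%

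The approximate 95% half-width is 1.96 × √(0.103 × 0.897 / 145) = 5.0 points. The overstatement runs from 0.1 points (d = 2) to 1.1 points (d = 14), well inside that width.

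**The case against.** The case for leaving the plan alone has several parts, and most of them limit the point rather than remove it.

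- **Do the Protocol and SAP conflict?** A reader might infer two different month-12 DSS results. The documents do not support that. The Protocol names no estimator for DSS and defers detail to the SAP, which fills the gap. A reader might also conclude that neither document's method can give the probability of cancer death. That fails too: the Protocol has no stated method to fault, and a simple proportion under complete 12-month follow-up would equal the cumulative incidence.
- **Does the SAP order other-cause deaths to be censored?** Not in words. Censoring is the natural result of the event definition combined with SAP 8.13. What the text itself shows is silence on competing deaths.
- **Are procedure-related deaths hidden?** It is tempting to say so, but they are absent only as events in the DSS curve. Overall survival, PFS and LTPFS count every death. SAP 8.11 tabulates all serious adverse events. Under Protocol 12.3 the DSMB reviews all reported deaths, and a death within 30 days puts enrollment on hold.
- **Is 10% early mortality realistic?** It comes from one death in 10 pilot subjects, who had primary NSCLC and were treated with a different navigation system. The sponsor then stopped that study to update the design. In this trial 10% would be 14 or 15 of 145 subjects. It is an extreme scenario and not a planning value.
- **Is Kaplan-Meier DSS simply conventional?** It is, and the SAP never calls it the proportion dying of cancer. This stands as a reason to keep the curve. It is not a reason to make it the only month-12 figure, since the absolute probability can be had from the same data.

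**Conclusion.** The point holds as a modest improvement to an untested secondary endpoint. As written, the SAP leads to a DSS curve in which other-cause deaths are censored, and 1 minus that curve overstates the month-12 probability of cancer death whenever such deaths precede cancer deaths.

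The direction follows from the estimator. The size depends on assumptions: about 0.2 to 0.8 points with 12-month mortality of 13-23%, constant hazards and 20-50% of deaths not from the cancer. It exceeds about 1 point only if early other-cause mortality is high. Beside a half-width of about 5 points this would not change how the trial is read, and it has no bearing on the Technique Efficacy test. The missing DSS entry in the Protocol lists is an omission to align.

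**What to change.** In SAP 8.8.2, make the main DSS figure the month-12 cumulative incidence of death from the treated malignancy, by the Aalen-Johansen estimator with a 95% interval. Treat death from any other cause, including procedure-related death, as a competing event, and censor only subjects alive at last contact. Show the cumulative incidence of other-cause death beside it; with every death assigned to one of the two categories, the parts add to 1 minus overall survival. State how deaths are classified, including those of unknown cause. Keep Kaplan-Meier DSS as a supplementary figure. Add DSS to the time-to-event lists in Protocol 10.9 and the Protocol Summary.

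The cost is a few sentences and one standard procedure. Protocol 5.7 already asks for records of the cause of death, and 12.1 asks for that cause to be reported. The downside is that the main figure is less directly comparable with published Kaplan-Meier DSS, which is why the supplementary curve stays. Settling this before database lock avoids choosing a method once causes of death are known.
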